6.3 Investigational drug administration

6.3.1 Before investigational product administration

Study treatment is stored refrigerated and should be allowed to warm to room temperature before administration. Prior to each IP administration:

- Investigator/authorised delegate will assess injection site as per standards of medical care;

- For FOCBP, urine pregnancy test will be done; IP will be administered only when the result of the test is negative. A FOCBP is defined as a premenopausal female capable of becoming pregnant.

6.3.2 Investigational product administration

The IP will be administered by the investigator/authorised delegate.

Investigational product should be administered into the upper arm, thighs, or the abdomen. It is suggested that the site of injection is rotated such that the patient receives IP at a different anatomical site at each treatment visit. Investigational product should not be administered into areas where the skin is tender, bruised, erythematous, or hardened.

6.3.3 After investigational product administration

After IP administration, the sponsor recommends that the patient should be observed for a minimum of 1 hour in case of any acute drug reactions.

6.3.4 Conditions requiring investigational product administration rescheduling

If any of the following occur, the investigator should reschedule the visit and the IP should not be administered until the rescheduled visit:

- The patient has an intercurrent illness, that in the opinion of the investigator may compromise the safety of the patient in the study (eg, viral illnesses);
- The patient is febrile ($\geq 38^{\circ}\text{C}$; $\geq 100.4^{\circ}\text{F}$) within 72 hours prior to the IP administration.

6.4 Measures to minimise bias: randomisation and blinding

Not applicable as this is an open-label study.

6.5 Treatment compliance

Any change from the dosing schedule and dose discontinuations should be recorded in the eCRF.

The IP Storage Manager is responsible for managing the IP from receipt by the study site until the destruction or return of all unused IP.

6.6 Concomitant therapy

Any medication or vaccine including over-the-counter or prescription medicines, vitamins, and/or herbal supplements that the patient is receiving at the time of enrolment or receives during the study must be recorded in the eCRF along with:

- Reason for use
- Dates of administration including start and end dates
- Dosage information including dose and frequency.

Restricted medications are listed in Table 4.

Table 4 Restricted medications

| Medication/class of drug: | Usage (including limits for duration permitted and special situations in which it's allowed): |
|--|---|
| Bronchodilator medication: SABA or SAMA Twice daily LABA or LAMA Once daily therapies containing LABA or LAMA | Should be withheld prior to scheduled spirometry for: 6 hours 12-24 hours ≥24 hours |
| Topical immunosuppressive medication | May be administered at the discretion of the investigator after discussion with the AstraZeneca Study Physician |
| Allergen immunotherapy injection | Should not be administered within 7 days of IP administration |
| Inactive/killed vaccines (eg, inactive influenza) | Should not be administered 7 days before or 7 days after IP administration |

Abbreviations: IP investigational product, LABA long-acting β 2 agonists, LAMA long-acting anti-muscarinic, SABA short-acting β 2 agonists, SAMA short-acting anti-muscarinic

Prohibited medications are listed in Table 5.

Table 5 Prohibited medications

| Prohibited medication/class of drug: | Duration |
|---|--|
| Immunosuppressive medication other than prior stable systemic corticosteroid for the maintenance treatment of asthma and for asthma exacerbations | Study period |
| Live attenuated vaccines | Within 30 days prior to first dose of IP, during the treatment period, and for 12 weeks (5 half-lives) after the last dose of IP |
| Oral or ophthalmic non-selective β -adrenergic antagonist (eg, propranolol) | Study period |
| Any marketed or investigational biologic (monoclonal or polyclonal antibody) | 4 months or 5 half-lives (whichever is longer) prior to Visit 1, during the treatment period, and 4 months or 5 half-lives (whichever is longer) after the last dose of the IP |
| Other IP | 30 days or 5 half-lives (whichever is longer) prior to first dose of IP and during the study period |

Abbreviations: IP investigational product

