8.1.1 Spirometry

8.1.1.1 General requirements

Lung function (FEV₁) at the study centre will be measured by spirometry using the site's own equipment. Spirometry should be performed by the investigator or authorised delegate according to American Thoracic Society/European Respiratory Society (ATS/ERS) guidelines (Miller et al 2005).

Important! Patients should withhold their bronchodilator medications prior to scheduled spirometry per Section 6.6. The patient's usual asthma medications may be administered following completion of the lung function procedures.

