3.1.4 Visit windows

Table 1 of the CSP detailed the time points and visit window for the study assessments. All summaries which are presented by time point will use a visit window to classify the data record, which is derived from the assessment date relative to the reference start date (date of first dose of study treatment). This approach allows appropriate classification of visits which may have occurred significantly earlier or later than the protocol assessment schedule, as well as the use of data captured at visits which have no fixed timing.

Inclusion within the visit window should be based on the actual date and not the intended nominal date of the visit.

Any data collected at unscheduled or repeat visits will be listed, and will be included in baseline definitions (Section 3.1.1), and in any definitions of maximum value, minimum value or last value within the relevant study period.

Data collected at unscheduled or repeat visits will also be included in visit windows, and therefore may be included in summaries by visit. In the case of a missing value at a scheduled visit, which is then followed by a non-missing value at an unscheduled or repeat assessment within the same visit window, the non-missing value at the unscheduled/repeat assessment will replace the missing value at the scheduled visit.

If a subject has more than one non-missing value within the same visit window, the following rules will apply:

- The non-missing value closest to the target day will be selected for analysis at that visit
- If two non-missing values are the same distance from the target day, the earlier of the two values will be selected for analysis at that visit
- If two non-missing values are recorded on the same day and have a different assessment time associated with both of them, the value with the earliest assessment time will be selected for analysis at that visit.
- If two non-missing values are recorded on the same day and have no assessment time associated with at least one of them, or the same assessment time associated with both of them, the average of the two values will be selected for analysis at that visit.
If a subject has no value within a particular visit window, then the subject will have a missing value at that visit in summaries.

Due to the overlap in the week 1 and 2 visit window schedule of assessments the following rules will apply subject to the above rules described in this section above:

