3.3.3 Pre-bronchodilator forced expiratory volume in first second (pre-BD FEV₁)

Change from baseline in pre-dose (when applicable), pre-bronchodilator, FEV₁ measured at Weeks 4, 8, 12, and 16 (Part A), and Weeks 24 and 48 (Part B) will be used as a secondary variable to evaluate the effect of benralizumab on pulmonary function.

The pre-BD FEV₁ will be measured by spirometry at the study centre.

Multiple forced expiratory efforts (at least 3 but no more than 8) will be performed for each centre spirometry session and the 2 best efforts that meet the American Thoracic Society (ATS)/ European Respiratory Society (ERS) acceptability and reproducibility criteria will be recorded in the eCRF. The best efforts will be based on the highest FEV₁. The absolute measurement (for FEV₁), and the percentage of predicted normal value will be recorded using the local spirometer at the site with predicted values derived from a reference value.

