4.2.9 Forced expiratory volume in first second (FEV1)

FEV₁ measurements and changes from baseline at each visit will be summarized using descriptive statistics for each treatment/weight group based on safety analysis set.

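### The SAP picks the FEV₁ visit value by date alone, so an unscheduled reading taken without bronchodilator withholding can stand as the pre-bronchodilator visit or baseline value (minor)

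*Protocol*

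**What the plan says.** **Endpoint.** SAP 3.3.3 defines the variable as "Change from baseline in pre-dose (when applicable), pre-bronchodilator" FEV₁ at Weeks 4, 8, 12, 16, 24 and 48.

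**Withholding.** Protocol 6.6, Table 4 lists 6 hours, 12–24 hours and at least 24 hours, depending on the drug class, under the words "Should be withheld prior to scheduled spirometry for". Protocol 8.1.1.1 repeats the limit: "Patients should withhold their bronchodilator medications prior to scheduled spirometry per Section 6.6".

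**Selection of values.** SAP 3.1.4 states: "Data collected at unscheduled or repeat visits will also be included in visit windows, and therefore may be included in summaries by visit". Where the scheduled value is missing, "the non-missing value at the unscheduled/repeat assessment will replace the missing value at the scheduled visit". Where several values exist in a window, the one nearest the target day is used and a tie goes to the earlier day. For two values on one day, the earlier time is used if the times differ; otherwise they are averaged. Unscheduled data also count towards baseline. SAP Table 1 applies windows to FEV₁, and no FEV₁ exception is given.

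**Analysis.** SAP 4.2.9 says only that FEV₁ "measurements and changes from baseline at each visit will be summarized" by treatment/weight group on the safety analysis set.

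**Data items.** For concomitant drugs, Protocol 6.6 asks for the reason, "Dates of administration including start and end dates", dose and frequency. Protocol 8.1.1.2 describes what is recorded for spirometry and does not name the time of the last bronchodilator.

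**The concern.** The endpoint's label carries a condition that the selection rule never tests. A scheduled reading has a withholding instruction behind it; an unscheduled one does not. The SAP treats the two as interchangeable and lets the calendar decide. The selected number can then be something other than the defined variable, and the by-visit table would not show it.

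The study has no control arm, so an error in a visit value passes directly into the reported mean change. An error in baseline passes, with opposite sign, into every later change for that child. The strata are small (at least 8 children each), so single values count.

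**Working it through.** The documents give no FEV₁ effect, SD or power figure, so there is no stated number to reproduce. The check is of the selection rule, with an illustration of size.

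**1. Can an unscheduled reading displace a valid scheduled one?** The rule minimises |day − target|, with ties going to the earlier day. At Week 16 the target is Day 112.

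- Scheduled Day 117: |117 − 112| = 5. Unscheduled Day 110: |110 − 112| = 2. The unscheduled reading is selected.
- Scheduled Day 115: distance 3. Unscheduled Day 109: distance 3. The tie goes to the earlier, unscheduled reading.

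So displacement does follow from the text.

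**2. How far does displacement reach?** Protocol Table 1 allows ±7 days for the post-baseline FEV₁ visits. If the scheduled reading is within that allowance, its distance is at most 7. Only an unscheduled reading also within 7 days of target can then win, whatever the width of the SAP window.

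**3. When do the wide windows matter?** Only when the scheduled value is missing or off-window. Width = last day − first day + 1. Days more than 7 from target = width − 15.

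| Visit | FEV₁ window (SAP Table 1) | Width | More than 7 days from target |
|---|---|---|---|
| Week 4 | 1–41 | 41 | 26 |
| Week 8 | 42–69 | 28 | 13 |
| Week 12 | 70–97 | 28 | 13 |
| Week 16 | 98–139 | 42 | 27 |
| Week 24 | 140–251 | 112 | 97 |
| Week 48 | 252 onward | 118 if follow-up ends on Day 369 (362 + 7) | 103 |

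With the scheduled value missing, a Week 24 reading may lie up to 251 − 168 = 83 days from target.

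**4. Is there a filter elsewhere?** SAP 3.3.3 and 4.2.9 have none. SAP 3.1.4 does prefer the scheduled value for PK samples taken on the same date, but not for FEV₁. The gap also covers a scheduled reading for which withholding was missed: no rule flags it or tests its effect.

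**5. Size, under assumptions not in the documents.** Take FEV₁ = 1.5 L and a reliever response of 5–15%.

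- Per reading: 0.05 × 1,500 = 75 mL to 0.15 × 1,500 = 225 mL.
- Shift in a visit mean = k × d / n, for k readings each raised by d.
- n = 8 (minimum stratum): one reading, 75/8 to 225/8, about 9–28 mL; two readings, about 19–56 mL.
- n = 30 (all children aged 6 to 11): one reading, 75/30 to 225/30, or 2.5–7.5 mL; two readings, 5–15 mL.

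**The case against.** The strongest reply is that the route may rarely be used. Protocol Table 1 schedules spirometry only at named visits. The protocol expressly allows extra ECGs and extra safety samples but does not mention extra spirometry, and it defines no exacerbation visit with a lung-function test. This stands: the frequency is unknown and may be zero. The SAP rule would still take in any unscheduled or repeat reading that is entered.

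A reader might infer that post-reliever readings cannot be identified. The documents do not support that. Unscheduled data are listed (SAP 3.1.4), drugs are recorded by date (Protocol 6.6), and receipt of a restricted treatment, which includes the Table 4 bronchodilators, is an example of an important protocol deviation (SAP 2.2). A suspect reading can be located. What the documents lack is a stated field or rule to confirm withholding to the hour. The eCRF is not available and may hold one.

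A reader might also infer that FEV₁ change would be biased upward. A reliever raises FEV₁, but a test done during worsening may read low, and a raised baseline reduces the change. The net direction is undetermined. Nor is the improvement of up to 159 mL in Protocol 2.2 a yardstick, since it comes from studies in patients aged 12 and over.

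Medians are reported beside means (SAP 4.1), which limits the pull of one value.

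Finally, restricting the main table to readings with documented withholding would have its own cost. It could remove children unable to go without relievers, probably the less well controlled, and so distort the mean change. That objection stands and shapes the fix.

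**Conclusion.** The concern holds in a limited form. SAP 3.1.4 can return, as the pre-bronchodilator FEV₁ at a visit or at baseline, a reading with no withholding requirement behind it, and can prefer it to a valid scheduled reading. This follows from a stated rule and is more than a missing detail. With the scheduled visit on time, the exposure is confined to unscheduled readings within 7 days of target; it widens to the full window when the scheduled value is missing or off-window.

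The size is about 9–28 mL per reading at n = 8 and 2.5–7.5 mL at n = 30, resting wholly on the assumed 1.5 L and 5–15% response and ignoring any fall from acute worsening. Severity is minor: the endpoint is secondary and descriptive, no hypothesis is tested, and neither the number of such readings nor the net direction of error can be determined from the documents.

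**What to change.** Change SAP 3.1.4 and 4.2.9, for FEV₁ only:

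- A non-missing scheduled value takes precedence over any unscheduled or repeat value in the window. This extends to the whole window the preference that the SAP already gives to scheduled PK samples on the same date.
- An unscheduled reading may fill a missing visit or baseline value only if it is documented as pre-bronchodilator according to Protocol Table 4.
- Same-day readings are not averaged where one is post-reliever.
- Readings with known missed withholding are flagged and listed. Scheduled readings of this kind stay in the main table, and a sensitivity table shows the FEV₁ summary without them.

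The cost is a few lines of SAP text, one sensitivity table, and a few visit values that become missing. No clinical rule changes. The protocol estimated last patient completion for September 2022 and the SAP amendment is dated 18 October 2022, so new eCRF fields for bronchodilator timing are probably too late. If the eCRF already captures the time of the last dose, it should be used to apply these rules; if not, the precedence rule can still be applied in full.

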6.6.1 Background medication

The patient's usual pre-study ICS and/or OCS formulations, doses and regimens, and any other additional allowed asthma controllers that they may have been taking prior to enrolment, should be continued throughout the screening and treatment periods. All changes in the patient's background medication should be documented in source along with the rationale for the change and recorded in the eCRF.

6.6.2 Other concomitant treatment

Other medication other than that described above, which is considered necessary for the patient's safety and wellbeing, may be given at the discretion of the investigator and recorded in the appropriate sections of the eCRF.

6.6.3 Rescue medication

Worsening of asthma symptoms should be treated according to standard practice.

6.7 Dose modification

No dose modification is allowed in this study. Patients aged 6 to 11 years will receive the same dose of benralizumab throughout the study based on their weight at screening. Patients aged 12 to 14 years will receive the  mg dose of benralizumab throughout the study.

6.8 Treatment after the end of the study

The patient should continue their usual asthma medication at the discretion of the investigator.

7 DISCONTINUATION OF TREATMENT AND SUBJECT WITHDRAWAL

7.1 Discontinuation of study treatment

Patients may be discontinued from IP in the following situations. Note that discontinuation from study treatment is NOT the same thing as a complete withdrawal from the study.

- Patient or guardian decision. The patient is at any time free to discontinue treatment, without prejudice to further treatment
- Adverse event
- Severe non-compliance with the CSP
- Eligibility requirement found not to be fulfilled
- Positive pregnancy test at any time during the study
- Lost to follow-up
- Development of any study specific criteria for discontinuation:
 - Anaphylactic reaction to the IP requiring administration of epinephrine

- Development of helminth parasitic infestations requiring hospitalization
- If 2 consecutive doses of IP are missed or more than 2 scheduled doses of IP are missed during Part A dosing
- An asthma-related event requiring mechanical ventilation.

See [Table 1](#) for data to be collected at the time of treatment discontinuation and follow-up and for any further evaluations that need to be completed.

7.1.1 Procedures for discontinuation of study treatment

A patient that decides to discontinue study treatment will always be asked about the reason(s) and the presence of any AEs. The date of last administration of study treatment should be documented in the eCRF. Patients permanently discontinuing study treatment should be given locally available standard of care therapy, at the discretion of the investigator.

All patients who prematurely discontinue IP should return to the study site and complete the procedures described for the Early Discontinuation (DXD) Visit within 4 weeks after the last dose of IP. At that visit, although no longer on IP, patients should be encouraged to remain in the study. Although only AEs, SAEs, and concomitant medication are required to be collected after the DXD Visit, safety data collection should continue according to the study protocol.

Note that in this case, the DXD Visit replaces the nearest regular visit while the following visits continue as possible. If the patient or guardian does not agree to continue in-person study visit(s), a modified follow-up, such as telephone contact with the patient or guardian, should be arranged to ensure the collection of safety information through the 48-week time point.

7.2 Lost to follow-up

A patient will be considered potentially lost to follow-up if he or she fails to return for scheduled visits and is unable to be contacted by the study site.

The following actions must be taken if a patient fails to return to the clinic for a required study visit:

- The site must attempt to contact the patient or guardian and reschedule the missed visit as soon as possible and counsel the patient on the importance of maintaining the assigned visit schedule.
- Before a patient is deemed lost to follow-up, the investigator or designee must make every effort to regain contact with the patient or next of kin by eg, repeat telephone calls, certified letter to the patient's or guardian's last known mailing address or local equivalent methods. These contact attempts should be documented in the patient's medical record.
- Efforts to reach the patient or guardian should continue until the end of the study. Should the patient be unreachable at the end of the study the patient should be considered to be

lost to follow-up with unknown vital status at end of study and censored at the latest follow-up contact.

7.3 Withdrawal from the study

A patient may withdraw from the study (eg, withdraw consent), at any time (IP and assessments) at his/her own request, without prejudice to further treatment.

If the patient withdraws consent for disclosure of future information, the sponsor may retain and continue to use any data collected before such a withdrawal of consent.

If a patient withdraws from the study, he/she or his/her guardian may request destruction of any samples taken, and the investigator must document this in the site study records.

A patient who withdraws consent will always be asked about the reason(s) and the presence of any AE. The investigator will follow-up patients as medically indicated.

See [Table 1](#) for data to be collected at the time of study discontinuation and follow-up and for any further evaluations that need to be completed.

If a patient withdraws from the study, then his/her enrolment code cannot be reused. Withdrawn patients may be replaced if they discontinue within Part A of the study.

8 STUDY ASSESSMENTS AND PROCEDURES

Study procedures and their timing are summarised in [Table 1](#).

The investigator will ensure that data are recorded in the eCRF. The Web Based Data Capture system will be used for data collection and query handling.

The investigator ensures the accuracy, completeness, legibility, and timeliness of the data recorded in the eCRF and of the provision of answers to data queries according to the Clinical Study Agreement. The investigator will sign the completed eCRF. A copy of the completed eCRF will be archived at the study site. Additional data to assess the impact of civil crisis, natural disaster, or public health crisis will be collected.

Immediate safety concerns should be discussed with the sponsor immediately upon occurrence or awareness to determine if the patient should continue or discontinue study treatment.

Adherence to the study design requirements, including those specified in [Table 1](#), is essential and required for study conduct.

All screening evaluations must be completed and reviewed to confirm that potential patients meet all eligibility criteria. The investigator will maintain a screening log to record details of

all patients screened and to confirm eligibility or record reasons for screening failure, as applicable.

Procedures conducted as part of the patient's routine clinical management and obtained before signing of the ICF may be utilised for screening or baseline purposes provided the procedures met the protocol-specified criteria and were performed within the time frame defined in [Table 1](#).

The recommended sequence for completion of assessments at each visit is:

- Complete ACQ-IA, PGIC-IA, CGIC
- Measure vital signs, ECG, conduct physical examination
- Conduct spirometry assessment
- Take blood samples
- Administer benralizumab.

Based on the European Medicines Agency's (EMA) Ethical Considerations for Clinical Trials on Medicinal Products Conducted with the Paediatric Population ([EMA 2008](#)), the maximum amount of blood collected, including any losses in the manoeuvre, from each patient should not exceed 3% of the total blood volume during a period of 4 weeks and should not exceed 1% at any single time during the study (Table 6).

Table 6 Maximum volume of blood to be withdrawn from a patient

| Patient weight (kg) | Total blood volume (mL) ^a | Maximum blood volume (mL) to be withdrawn at any visit | Maximum blood volume (mL) to be withdrawn within a 4-week period |
|---------------------|--------------------------------------|--|--|
| 15-20 | 1200-1600 | 12.0-16.0 | 36.0-48.0 |
| 21-25 | 1680-2000 | 16.8-20.0 | 50.4-60.0 |
| 26-30 | 2080-2400 | 20.8-24.0 | 62.4-72.0 |
| 31-35 | 2480-2800 | 24.8-28.0 | 74.4-84.0 |
| 36-40 | 2880-3200 | 28.8-32.0 | 86.4-96.0 |
| 41-45 | 3280-3600 | 32.8-36.0 | 98.4-108.0 |
| 46-50 | 3680-4000 | 36.8-40.0 | 110.8-120.0 |
| 51-55 | 4080-4400 | 40.8-44.0 | 122.4-132.0 |
| 56-60 | 4480-4800 | 44.8-48.0 | 134.4-144.0 |
| 61-65 | 4880-5200 | 48.8-52.0 | 146.4-156.0 |
| 66-70 | 5280-5600 | 52.8-56.0 | 158.4-168.0 |
| 71-75 | 5680-6000 | 56.8-60.0 | 170.4-180.0 |
| 76-80 | 6080-6400 | 60.8-64.0 | 182.4-192.0 |

Table 6 Maximum volume of blood to be withdrawn from a patient

| Patient weight (kg) | Total blood volume (mL) ^a | Maximum blood volume (mL) to be withdrawn at any visit | Maximum blood volume (mL) to be withdrawn within a 4-week period |
|---------------------|--------------------------------------|--|--|
| 81-85 | 6480-6800 | 64.8-68.0 | 194.4-204.0 |
| 86-90 | 6880-7200 | 68.8-72.0 | 206.4-216.0 |
| 91-95 | 7280-7600 | 72.8-76.0 | 218.4-228.0 |
| 96-100 | 7680-8000 | 76.8-80.0 | 230.4-240.0 |

^a The total blood volume is estimated at 80 mL/kg body weight.

Source: [EMA 2008](#)

The total maximum volume of blood that will be withdrawn from each patient at each study visit is listed in Table 7.

Table 7 Maximum volume of blood to be withdrawn from each patient

| Visit | Samples required | Total maximum volume (mL) ^a |
|-----------------------------|---|--|
| Visit 1 (Screening) | clinical chemistry; haematology; serology | 13.0 |
| Visit 2 | PK; ADA | 5.0 |
| Visit 3 | PK | 2.5 |
| Visit 4 | PK | 2.5 |
| Visit 5 | PK | 2.5 |
| Visit 6 | clinical chemistry; haematology; PK | 7.0 |
| Visit 7 | clinical chemistry; haematology; PK; ADA | 9.5 |
| Visit 8 | clinical chemistry; haematology; PK | 7.0 |
| Visit 9 | clinical chemistry; haematology; PK; ADA | 9.5 |
| Visit 10 | clinical chemistry; haematology; PK; ADA | 9.5 |
| Visit 11 | | 0 |
| Visit 12 | | 0 |
| Visit 13 (End of Treatment) | clinical chemistry; haematology; PK; ADA | 9.5 |
| Visit 14 (Follow-up) | | 0 |
| Early discontinuation (DXD) | clinical chemistry; haematology; PK; ADA | 9.5 |
| Total (mL) | | 87.0 |

^a Volumes exclude serum pregnancy testing and excludes any re-testing requirements. If serum pregnancy testing is needed, it will be analysed from samples collected at Visit 1, Visit 6, Visit 7, Visit 8, Visit 9, Visit 10, Visit 13, and the DXD Visit. If serum pregnancy testing is to be analysed at other visits then an additional 2.5mL blood collection will be required.

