^a The screening clinical chemistry/haematology samples at Visit 1 (Day -28 to Day -14) will constitute baseline values provided that Visit 2 (Day 0) is done ≤ 28 days after Visit 1. If so, no safety laboratory samples will need to be collected at Visit 2.

^b To be performed before IP is administered at these visits.

Abbreviations: ACQ-IA interviewer-administered asthma control questionnaire, ADA anti-drug antibody(ies), CBC complete blood count, CGIC clinician global impression of change, DXD early discontinuation, ECG electrocardiogram, exam examination, EOT end of treatment, FEV₁ forced expiratory volume in 1 second, F/U follow-up, HIV human immunodeficiency virus, IP investigational product, PD pharmacodynamics, PE physical examination, PGIC-IA interviewer administered patient global impression of change, PK pharmacokinetics, SCRN screening, std standard, WD early withdrawal.

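### The 13.0 mL maximum at Visit 1 in Table 7 exceeds the protocol's own 1% single-draw limit for eligible children of 15 to under 16.25 kg

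*Protocol*

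**What the plan says.** Protocol Section 8 adopts two limits from European paediatric ethics guidance. Over four weeks, no more than 3% of total blood volume may be taken; for a single collection, the amount "should not exceed 1% at any single time during the study". Both limits count the blood "including any losses in the manoeuvre".

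Table 6 turns these percentages into volumes by weight. Its footnote gives the basis: "The total blood volume is estimated at 80 mL/kg body weight". The lowest row reads "15-20 | 1200-1600 | 12.0-16.0 | 36.0-48.0" (weight in kg, then total blood volume, per-visit limit and 4-week limit in mL). Section 5.1, criterion 9, admits children from 15 kg, so the bottom of that row is a weight the trial can enrol.

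Table 7 then sets out the planned volumes: "The total maximum volume of blood that will be withdrawn from each patient at each study visit is listed in Table 7". Its Visit 1 (Screening) row is "clinical chemistry; haematology; serology | 13.0". The figure is not scaled by weight. The Table 7 footnote deals only with serum pregnancy testing and re-testing.

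**The concern.** A maximum stated for each patient at a visit should be permissible for every patient the trial can enrol. At 15 kg, Table 6 permits 12.0 mL and Table 7 permits 13.0 mL. The protocol text available does not say which governs, and it provides no reduced volume or split collection for the lightest children.

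What is at stake is a child-protection limit that the protocol sets for itself. A site that plans its screening draw from Table 7 alone could exceed the limit in a very light child without any warning. No endpoint, estimate or analysis depends on this.

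**Working it through.** **Inputs (all from the protocol)**
- Single-collection limit: 1% of total blood volume (Section 8).
- 4-week limit: 3% (Section 8).
- Blood volume: 80 mL/kg (Table 6 footnote).
- Minimum weight: 15 kg (Section 5.1, criterion 9).
- Visit volumes: Table 7.

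**Reproducing the plan's figures.** Per-visit limit = 0.01 × 80 × weight = 0.8 mL/kg. At 15 kg this is 12.0 mL and at 20 kg it is 16.0 mL, as Table 6 prints. The Table 7 volumes sum to 13.0 + 5.0 + 3 × 2.5 + 7.0 + 9.5 + 7.0 + 9.5 + 9.5 + 9.5 + 9.5 = 87.0 mL, as stated.

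**Visit 1 against the limit, if the full 13.0 mL is drawn**

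| Weight (kg) | Blood volume (mL) | 1% limit (mL) | Excess (mL) | 13.0 mL as % of volume |
|---|---|---|---|---|
| 15 | 1200 | 12.0 | 1.0 | 1.083 |
| 15.5 | 1240 | 12.4 | 0.6 | 1.048 |
| 16 | 1280 | 12.8 | 0.2 | 1.016 |
| 16.25 | 1300 | 13.0 | 0 | 1.000 |
| 17 | 1360 | 13.6 | none | 0.956 |

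Break-even weight = 13.0 / 0.8 = 16.25 kg, so the affected band is 15 kg to under 16.25 kg.

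**Other visits.** The next largest volume in Table 7 is 9.5 mL. At 15 kg that is 9.5 / 1200 = 0.79%, and it would meet the limit down to 9.5 / 0.8 = 11.875 kg.

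**Visit 2 with repeated safety samples.** Footnote a of Table 1 waives safety samples at Visit 2 when it falls within 28 days of Visit 1: "If so, no safety laboratory samples will need to be collected at Visit 2". If it falls later, chemistry and haematology are added. Their volume can be inferred from Visit 6 less its PK sample: 7.0 − 2.5 = 4.5 mL. Visit 2 then comes to 5.0 + 4.5 = 9.5 mL, which complies.

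**4-week limit.** Visits 1 to 5 total 13.0 + 5.0 + 3 × 2.5 = 25.5 mL, or 25.5 / 1200 = 2.125% at 15 kg, against 36.0 mL (3%). This complies.

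**The case against.** The arithmetic is not in dispute. The case on the other side concerns what follows from it.

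- **Both tables state ceilings.** When two ceilings apply to the same child, the lower one can be taken to govern, and the Table 6 rule comes just before Table 7 in the same section. It stands that a site can satisfy both by drawing less. But Table 7 is the plan for each visit, and its stated maximum should itself be allowable for every eligible child.
- **There is some flexibility at screening.** Section 8 lets suitable routine results obtained before consent serve for screening, and nothing expressly forbids splitting the collection. The first is optional, and Section 8.2.1's central-laboratory requirement narrows it. The second is not provided for, and Table 6 sets its limit per visit. Neither is a safeguard tied to weight.
- **The Laboratory Manual may already specify smaller tubes.** It was not available, so this cannot be excluded. The two protocol tables would still disagree.
- **The effect is tiny.** The excess is at most 1.0 mL, or 0.083 percentage points of an estimated blood volume, under a limit worded as a recommendation, in children aged 6 or over who weigh less than 16.25 kg. This stands and bounds the importance of the point.
- **The correction may come late.** The SAP dates protocol version 5.0 to 22 February 2022, and the synopsis estimates last patient completion in September 2022. Counting back 56 weeks puts the last screening visit around August to September 2021. If those estimates held, an amendment to version 5.0 would protect few or no further children. They are only estimates, and the tables would still conflict.

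**Conclusion.** The concern holds. On the protocol's own inputs, the Visit 1 maximum in Table 7 is above the Table 6 limit for children of 15 to under 16.25 kg, by at most 1.0 mL (1.083% of blood volume instead of 1%). Every other visit and the 4-week total comply.

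The size of the excess assumes that the full 13.0 mL is drawn and that this figure already includes losses. Table 7 does not say whether it does; if not, the affected band reaches somewhat above 16.25 kg. Re-testing at the same visit, which Table 7 leaves out, would also add volume. The documents do not give the expected number of children in the band, and it could be zero.

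This is a minor inconsistency in a paediatric safety limit. It should be corrected because the correction is nearly free. It is not evidence of harm and has no bearing on the results.

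**What to change.** Add a footnote to the Visit 1 row of Table 7 stating that the Table 6 limit prevails, and that for children under 16.25 kg the Visit 1 draw, losses included, must not exceed 0.8 mL/kg (12.0 mL at 15 kg). That footnote resolves the conflict on its own. A matching line in the Laboratory Manual, with smaller tube volumes for these children if it does not already have them, would make it workable at sites.

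The cost is one footnote and one manual line. Endpoints, sample size and visit schedule are unchanged.
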